5.8.6. Analysis of Vital Signs

For respective treatment period (DBTP and SBTP), the vital sign actual values and change from baseline values obtained while sitting will be descriptively summarized at baseline and each post-baseline visit (collected up to the day of last dose of study treatment +28 days) by at least patient number, mean, median, Q1, Q3, SD, minimum and maximum. Vital sign mean changes from baseline, with the corresponding SE, can be plotted at each visit in the case results warrant further investigation.

Individual patient vital sign measurements (regardless of sitting position) will be additionally evaluated by PCSV criteria, specifically identifying patients with at least one post-baseline measurement that meets the PCSV criteria within the TEAE period. The incidence of PCSVs at any time during the respective TEAE periods will be summarized regardless of the baseline level, and again according to the following baseline categories:

- Normal (according to PCSV criterion/criteria)/missing
- Abnormal according to PCSV criterion or criteria

Patient listings of vital sign measurements that meet PCSV criteria will be provided for the report appendix.

5.8.7. Analysis of 12-Lead ECG

For respective treatment period (DBTP and SBTP), ECG parameters will be described through an overall interpretation of ECG status (e.g. normal, abnormal [clinically significant (Yes/No)]). The count and percentage of patients with at least 1 abnormal post-baseline ECG during the respective TEAE period will be summarized according to the following baseline status categories:

- Normal/missing;
- Abnormal

5.8.8. Physical Exams

A list of patients with any clinically significant abnormality results will be generated.

5.9. Analysis of Pharmacokinetic Variables

Descriptive statistics for concentrations of total evinacumab and total ANGPTL3 will be presented. Mean concentrations of each analyte will be tabulated by visit and treatment group, with concentrations below the LLOQ set to zero.

Plots of the mean concentrations (linear and log scales) will be presented by nominal sampling time. Plots of the individual concentrations (linear and log scales) will be presented by actual sampling time. In the linear-scaled plots, concentrations below the LLOQ will be set to zero; in the log-scaled plots, concentrations below the LLOQ will be imputed as LLOQ/2.

When appropriate, relationship between concentrations of evinacumab and concentration of total ANGPTL3 (target engagement), percentage of TG reduction or other biomarkers may be evaluated descriptively.

5.10. Analysis of Anti-evinacumab Antibody Variables

The ADA variables described in Section 4.10 will be summarized using descriptive statistics by dose/cohort group in the ADA analysis set. Listings of ADA positivity and titers presented by patient, time point, and study treatment received will be provided. Incidence of treatment-emergent ADA will be assessed as absolute occurrence (N) and percent of patients (%), grouped by study treatment received.

The influence of ADA on drug concentrations will be evaluated. Assessment of impact of ADA on safety and efficacy may be provided.

Anti-drug antibody status (negative or positive) and titer over the study duration may be classified as follows:

- Negative - negative in the ADA assay at all time points
- Pre-existing immunoreactivity - a positive response in the ADA assay at baseline with all post first double-blind dose results negative in the ADA assay, or a positive response at baseline with all post-first dose responses less than 9-fold of the baseline titer levels

- Treatment emergent response is defined as a positive response in the ADA assay post first double-blind dose when baseline results are negative or missing. The treatment emergent responses will be further characterized as Persistent, Indeterminate or Transient and further categorized as follows:
 - Persistent - Treatment emergent ADA positive response with two or more consecutive ADA positive sampling time points separated by greater than 16-week period (based on nominal sampling time), with no ADA negative samples in between, regardless of any missing samples.
 - Indeterminate - A positive result in the ADA assay at the last collection time point analyzed only, regardless of any missing samples
 - Transient - a treatment emergent ADA positive assay response that is not considered persistent or indeterminate regardless of any missing samples
- Treatment boosted response - defined as a positive response in the ADA assay post first dose, that is at least 9-fold over baseline titer levels when baseline results are positive
- Titer category for subjects, by maximum ADA titer value:
 - Low (titer <1,000)
 - Moderate (1,000≤ titer ≤10,000)
 - High (titer >10,000)
- NAb status (positive or negative)

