8.2.6.2. Anti-Drug Antibody Measurements and Samples

Serum samples for ADA assessment will be collected at time points listed in Table 1. They will be collected pre-dose on days when study drug is administered.

Patients who exhibit a treatment emergent or treatment boosted positive ADA assay response in their last sample analyzed will be followed until the titers are less than 240 or within 2 dilution steps from the pre-dose baseline titer levels.

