2.3. Study Plan

The study consists of a screening period of up to 37 days (which includes day -66 to day -59 [visit 1], day -58 to -52 [visit 1b], and day -51 to -39 [visit 2]), a placebo run-in period (day -28 to day -1), a 12-week double-blind treatment period (day 1 to day 85), a single-blind 12-week evinacumab treatment period (day 86 to day 169), and an off-treatment follow-up period (week 24 [day 170] to week 44 [day 309]).

A study flow diagram is in [Figure 1](#).

Figure 1: Study Flow Diagram

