7. TIMING OF STATISTICAL ANALYSES

The analyses will be conducted in 2 steps:

- First step: Main Efficacy and Safety Analysis

The first analysis will be conducted when all enrolled patients have completed the double-blind period. This will consist of the final analysis of the primary and secondary endpoints up to week 12. The safety analysis will be performed on all safety data collected and validated at the time of the first analysis.

- Second-step: Final Efficacy and Safety analysis

The second analysis will be conducted at the end of the study and will consist of the final analysis of week 44 efficacy endpoints and final safety analysis

Interim Analyses

Interim analyses may be conducted during the course of the study by the unblinded team to assess efficacy, safety, and futility. If the timing of this analysis falls within a few weeks of the first-step analysis, only the first-step analysis will be performed. Enrollment (up to a maximum of approximately 50 patients) may be halted if the incidence of pancreatitis is much lower than anticipated, making the evaluation of a treatment effect on pancreatitis futile. The following interim analysis is planned:

- The interim analysis will be conducted when the first 9 randomized patients have been administered study treatment in cohort 1 and have completed the double-blind period (i.e., week 12 visit). This will consist of the final data contributing to the analysis of the applicable variables up to week 12 for these 9 patients. In general, interim analysis will include only limited number of outputs applicable for the small sample size. For lipid variables, only descriptive summaries (without within-patient tests) in conventional units will be provided. Other variables (defined in Section 4.7.3) biomarkers, ECG, and PRO variables will not be included. Imaging and PK/ADA may be included in the analyses depending on the availability. For general labs and vital signs only PCSV summary tables will be included. The safety analysis will be performed for these 9 patients on all safety data collected and validated at the time of the first interim analysis. The interim analysis results will be used for the future program development.

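### SAP 5.10 labels some patients who are still ADA-positive at their last analysed sample as Transient, because Indeterminate covers only a lone last positive

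*SAP*

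**What the plan says.** Protocol 4.4 leaves the definitions of persistent and transient ADA to the SAP, so SAP 5.10 is the only place where they are set. There, a treatment-emergent response is "a positive response in the ADA assay post first double-blind dose when baseline results are negative or missing", and such responses are then divided into three classes:

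- **Persistent:** two or more consecutive positive time points "separated by greater than 16-week period (based on nominal sampling time), with no ADA negative samples in between".
- **Indeterminate:** "A positive result in the ADA assay at the last collection time point analyzed only, regardless of any missing samples".
- **Transient:** the residual class, which takes every treatment-emergent response that fits neither of the other two, whether or not samples are missing.

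The schedules of events (Protocol Table 1; SAP Appendix 10.4) place ADA samples at day 1 before dosing, then at weeks 4, 12, 24 and 44.

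SAP 7 makes the first-step analysis the final one for primary and secondary endpoints up to week 12. ADA is among the secondary endpoints in Protocol 4.2.2. For the cohort 1 interim, also on data to week 12, SAP 7 says: "Imaging and PK/ADA may be included in the analyses depending on the availability".

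Protocol 8.2.6.2 adds that patients with a treatment-emergent or boosted "positive ADA assay response in their last sample analyzed will be followed until the titers are less than 240" or have come back close to the pre-dose level.

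**The concern.** A three-way persistence rule should place a patient whose last sample is positive, and whose follow-up is too short or too broken to show persistence, in the undecided class. The word only in the Indeterminate definition prevents this. A patient with one positive, at the last sample, is undecided. A patient with that same positive plus an earlier one that does not complete a 16-week run drops into the residual class, Transient. More evidence of antibody can therefore give the milder-sounding label.

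The rule also sits awkwardly beside Protocol 8.2.6.2, which treats a positive last sample as unfinished business. What is at stake is the accuracy of the persistence subclasses in a secondary-endpoint analysis, and of any descriptive use made of them. SAP 5.10 plans to evaluate the influence of ADA on drug concentrations, although it does not specify that by persistence class.

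**Working it through.** The plan states no figure to reproduce, so the check applies the SAP 5.10 rules to every positive/negative pattern.

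**Inputs.** Post-dose ADA samples at weeks 4, 12, 24 and 44 (days 29, 85, 169 and 309) from the schedules of events; the class rules from SAP 5.10.

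**Nominal separations** (difference in days divided by 7):

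- Weeks 4 to 12: (85 − 29)/7 = 8 weeks
- Weeks 12 to 24: (169 − 85)/7 = 12 weeks
- Weeks 24 to 44: (309 − 169)/7 = 20 weeks
- Weeks 4 to 24: (169 − 29)/7 = 20 weeks
- Weeks 12 to 44: (309 − 85)/7 = 32 weeks

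**Classification.** Separation is taken as first to last positive of an unbroken run. With k samples there are 2^k − 1 patterns with at least one positive. P, I and T stand for Persistent, Indeterminate and Transient.

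| Samples analysed | Positive patterns | P / I / T as written | T with last sample positive | P / I / T after the fix |
|---|---|---|---|---|
| Weeks 4, 12 | 3 | 0 / 1 / 2 | `++` | 0 / 2 / 1 |
| Weeks 4, 12, 24 | 7 | 1 / 1 / 5 | `-++`, `+-+` | 1 / 3 / 3 |
| Weeks 4, 12, 24, 44 | 15 | 5 / 1 / 9 | `++-+`, `+--+`, `-+-+` | 5 / 4 / 6 |

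Row by row:

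1. **Data to week 12.** The longest run is 8 weeks, so Persistent is impossible. `-+` is Indeterminate; `++`, positive at every post-dose sample, is Transient.
2. **Last sample at week 24.** `--+` is Indeterminate. `-++` has a 12-week run and two positives, so it is Transient. The same holds if week 4 is missing rather than negative. `+-+` is Transient because a negative breaks the run.
3. **All four samples.** The three affected patterns are all negative at week 24 and positive again at week 44.

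**Boundary of the problem.** Any sample before week 44 precedes it by at least 20 weeks. So whenever week 44 is present and the last two analysed samples are both positive, the patient is Persistent. That covers all 4 complete-data patterns and, allowing missing earlier samples, all 13 patterns of this kind.

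**Other reading.** If separation means the gap between adjacent samples, every case above stands. `+++` ending at week 24 also becomes Transient, and the complete-data counts become 4 / 1 / 10.

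**The case against.** The strongest reply is that the rule works for patients who complete the schedule. Someone positive at the last two scheduled samples is Persistent, so a reader who inferred that two final positives always yield Transient would be wrong. The three affected complete-data patterns are intermittent, and some would accept Transient for them.

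Early leavers are mostly covered too. Protocol 7.4.2 and 8.1.2 provide early-termination assessments and then a final visit about 24 weeks after stopping, and the end-of-study visit includes ADA. Only patients who also lack that sample are exposed. Protocol 8.2.6.2 keeps following those with a positive last sample, although the SAP does not say how the extra samples enter the classes.

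A reader might also infer that continuing immunogenicity is reported as resolved. The SAP never equates Transient with resolved, and it lists positivity and titer by patient and time point. Nor is ADA incidence understated: SAP 1.2.2 and 5.10 count treatment-emergent responses, whatever their subclass.

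At week 12, no 16-week rule could be met. The lead-in in SAP 5.10 makes the classification optional and refers to the whole study. The interim concerns 9 patients. For patients randomised to placebo, the weeks 4 and 12 samples precede any evinacumab.

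All of that narrows the point. What remains is that the treatment-emergent item itself is worded as mandatory, SAP 7 carries the SAP's methods into the interim and first-step analyses with no exception for ADA, and the inversion at week 12 and with week 44 missing follows from the text. If only was meant in another sense, the sentence is ambiguous and still needs rewording.

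**Conclusion.** The point holds in limited form. As written, SAP 5.10 assigns Transient to some patients positive at their last analysed sample: `++` at a week-12 cut; `-++` or `+-+` when there is no week-44 sample; and `++-+`, `+--+` or `-+-+` on complete data. It does not misclassify patients positive at both weeks 24 and 44.

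The effect is confined to the descriptive persistence subclasses and probably to few patients. The documents give neither an ADA incidence nor a missing-sample rate, so 1 of 3, 2 of 7 and 3 of 15 count possible patterns and are not expected frequencies. The conclusion assumes nominal sampling times, as the SAP prescribes, and that only means the last sample is the sole positive. It merits correction because the definitions are set nowhere else and the change is small.

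**What to change.** Change two definitions in SAP 5.10:

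- Indeterminate: treatment-emergent ADA positive at the last time point analysed and not meeting the Persistent criterion.
- Transient: treatment-emergent, not Persistent, and negative at the last time point analysed.

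Add to SAP 7 that the week-12 interim and first-step analyses report only treatment-emergent status and titer, without the persistence classes.

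The Persistent class is unchanged. The cost is a short text edit and a small programming change. A few patients move from Transient to Indeterminate, which looks slightly less favourable.

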5.11. Analysis of PRO Variables

Descriptive statistical analyses for the PRO variables defined in Section 4.11 will be summarized by treatment group and overall for the study, as well as by treatment group and overall within each cohort in the PRO population.

Only measurements collected within 14 days prior to the protocol scheduled time point (as defined by e-CRF visit label) will be assigned to that visit and used for the analyses. If more than 7 days of data are collected during this period, only 7 days of the data (closest to the visit date) will be used. PRO evaluation at the visit is considered non-missing if a patient completes the questionnaire for at least four days for this visit. Missing PRO evaluations will not be imputed.

A cross-sectional analysis will be performed for each available PRO variable for the SBTP and the DBTP. The HAP-SS and HAP-DB domains and total scores including change from baseline will be reported at each time point. The number of patients with non-missing values, mean, standard deviation, median, Q1, Q3, minimum value, and maximum value will be reported. Summaries for the DBTP will be presented by treatment groups (evinacumab, placebo). Summaries for the SBTP will be presented by all patients and by treatment group in DBTP (i.e., evinacumab, placebo).

During the DBTP the difference in change score from baseline between the treatment groups will be calculated and presented as the number of patients with non-missing values, mean, 95%

confidence interval (if data is normally distributed), standard error, median, Q1, Q3, minimum value, and maximum value at each time point. No formal inferential testing will be performed. Summaries will be descriptive in nature.

The number and percentage of stomach pain, pain, and abdominal symptom free days, and avoidance of meals, at each evaluation/visit (calculated over the seven days prior to the visit), will be presented at each time point for all patients (SBTP) and for each treatment arm (DBTP). To take account of varying numbers of completed HAP-SS and HAP-DB scores over the seven days prior to each visit (minimum number = 4, maximum number = 7), percentage scores will be calculated using both a denominator of 7 and a denominator of the number of days of available data.

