4.2.2. Secondary Endpoints

The secondary endpoints of the study are:

- Percent TG lowering from baseline following 2 to 24 weeks of repeated IV doses of evinacumab overall and subgroups with homozygous or compound heterozygous LOF mutations, heterozygous LOF mutations, and without LOF mutations in genes in the LPL pathway
- Changes in patient reported abdominal and GI symptoms, dietary habits, and symptom/dietary impact measures

- Degree of pancreatic injury/inflammation through ¹⁸F-FDG-PET imaging at baseline (placebo run-in) and change from baseline following 12 weeks of treatment with evinacumab as assessed by ¹⁸F-FDG standardized uptake values SUV_{max} and SUV_{mean}
- Degree of pancreatic injury/inflammation through DW-MRI at baseline (placebo run-in period) and the change from baseline following 12 and 24 weeks of treatment with evinacumab as assessed by ADC
- The total evinacumab concentrations, total ANGPTL3 concentrations, and ADA during the evinacumab treatment and follow-up periods
- Incidence and severity of treatment-emergent adverse event (TEAEs), SAEs, laboratory abnormalities, and other safety variables in patients treated with evinacumab

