2. INVESTIGATION PLAN

2.1. Study Design and Randomization

This is a phase 2, randomized, placebo-controlled, study designed to evaluate the efficacy and safety of repeated doses of evinacumab in adult patients with severe HTG. Up to approximately 50 patients will be enrolled, randomized 2:1 (evinacumab:placebo) to receive evinacumab 15 mg/kg IV every 4 weeks (Q4W) or matching placebo IV Q4W for the 12-week double-blind treatment period (DBTP). After completion of the DBTP, all patients will enter a 12-week single-blind treatment period (SBTP) and receive open-label evinacumab 15 mg/kg IV Q4W. Investigators, Regeneron Study Director, Medical Monitor, Study Monitor, and any other Regeneron and contract research organization (CRO) personnel who are in regular contact with the study site will be blinded to treatment assignment during the double-blind treatment period of

the study and blinded to blood lipid measurements during the double-blind and single-blind treatment periods. After SBTP, all patients will undergo a 24-week follow-up after the last dose of study treatment.

The following cohorts will be enrolled based upon information (or lack of information) on genotype in the patient's medical history at screening:

1. Cohort 1: FCS due to complete LPL deficiency. Approximately 6 to 9 patients will be enrolled. This cohort consists of patients:
 - with known homozygous or compound heterozygous null LPL, GPIHBP1, or APOC2 LOF mutations
2. Cohort 2: Multifactorial chylomicronemia with partial LPL deficiency. Approximately 9 to 12 patients will be enrolled. This cohort consists of patients:
 - with known heterozygous null LPL, GPIHBP1, or APOC2 LOF mutations, or
 - with uncharacterized or known non-null LOF LPL pathway gene mutations (LPL, apoC2, apoA5, LMF1 and GPIHBP1)
3. Cohort 3: Multifactorial chylomicronemia. Approximately 15 to 27 patients will be enrolled. This cohort consists of patients not included in cohorts 1 or 2 above:
 - with other monogenic or polygenic causes of sHTG (eg, CGKR, CREB3L3, E2/E2 dysbetalipoproteinemia), or
 - without genotype information

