3.6. Patient-Reported Outcomes (PRO) Analysis Set

The analyses of the PRO data in the respective treatment period (DBTP and SBTP) will be performed on all randomized patients who received any double-blind study treatment with a baseline and at least 1 non-missing post-baseline PRO evaluation. Treatment assignments for the DBTP are based on the treatment received (placebo or evinacumab).

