4.11. PRO Variables

The baseline value is defined as the last available measurement prior to the date of the first double-blind study treatment administration (applicable to measurement derivations during both DBTP and SBTP).

The patient experience of symptoms and the impact on dietary behavior will be assessed with two de novo PRO measures: the Hypertriglyceridemia and Acute Pancreatitis Symptoms Scale (HAP-SS) and the Hypertriglyceridemia and Acute Pancreatitis Dietary Behavior questionnaire (HAP-DB).

- Hypertriglyceridemia and Acute Pancreatitis Symptom Scale (HAP-SS)

The HAP-SS is a 19-item measure of symptoms that has a 24-hour recall period. Four pain items are captured on a 0-10-point severity NRS, each scored 0='No pain' to 10='Worst possible pain', while the 15 non-pain items are captured on a 5-point frequency Likert scale, each scored from 1='None of the time' to 5='All of the time'. The proposed structure of the measure is currently being tested and is yet to be finalized but currently consists of a total score and four domain scores: pain; abdominal symptoms; physical symptoms; other symptoms, each scored 0 (no symptoms) to 100 (severe symptoms).

The Pain domain includes the four items: item 1 - stomach pain average, item 2 - stomach pain at worst, item 3 - back pain at worst, item 4 - stomach pain after eating (possible score range: 0 to 40).

The Abdominal symptoms domain includes the 6 items: item 5 – bloated or swollen stomach, item 6 – nausea/feeling sick, item 7 – vomiting, item 8 – passed excessive gas, item 9 – loose stools/diarrhoea, item 10 – foul smelling, light-coloured or greasy stool (possible score range: 6 to 30).

The Physical symptoms domain includes 5 items: item 11 – fever or flu like symptoms, item 12 - insomnia, item 13 – excessive sweating, item 14 – dizziness (lightheadedness), item 15 - racing heart rate (felt like your heart was racing) (possible score range 5 to 25).

The Other symptoms domain includes 4 items: item 16 – fatigue, item 17 – loss of appetite, item 18 – been hungry after eating, item 19 – felt full after eating a small amount (possible score range 4 to 20).

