Each item will be calculated at each evaluation/visit as the mean of the item scores over the seven days previous to the visit; each domain score at each evaluation/visit will be calculated as the sum of the mean component item scores. Each domain score will then be transformed onto a 0-100 scale, with the total score being the sum of the four domain scores (0-400), also then transformed to a 0-100 scale.

To transform to a 0-100 scale the following algorithm will be applied:

Transformed score = $100 \times (\text{score} - \text{minimum possible score}) / (\text{maximum} - \text{minimum possible score})$.

- Dietary behavior questionnaire (HAP-DB)

The HAP-DB is a 6-item measure of dietary behavior that has a 24-hour recall period. The items in the measure are all captured on a 5-point frequency Likert scale, each scored from 1='None of

the time' to 5='All of the time'. The proposed structure of the measure is currently being tested and is yet to be finalized but currently consists of a dietary impact total score, ranging from 6 (no impact) to 30 (severe impact).

The six HAP-DB items are: item 1 – amount of food eaten, item 2 – fatty or greasy food, item 3 – carbohydrates, item 4 – sugar or sugary foods, item 5 – alcohol intake, item 6 – skipped meal.

Each item will be calculated at each evaluation/visit as the mean of the item scores over the seven days previous to the visit. The total score will be calculated as the sum of the six item scores and then transformed to a 0-100 score.

To transform to a 0-100 scale the following algorithm will be applied:

Transformed score = $100 \times (\text{score} - \text{minimum possible score}) / (\text{maximum} - \text{minimum possible score})$.

4.11.1. Number of pain and abdominal symptom free days and days where meals are avoided

Exploratory endpoints of the frequency of stomach pain (on average, and at its worse), pain (stomach pain, back pain, stomach pain at its worst after eating), and abdominal symptom free days at each evaluation/visit will be defined as the number and percentage of stomach pain free days, number and percentage of pain free days, and the number and percentage of abdominal symptom free days over the seven days prior to the visit, as assessed by the HAP-SS:

- A stomach pain free day will be determined if the patient scores 0 - 'No Pain' on both of the HAP-SS stomach pain items 1 and 2.

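### The randomised PRO difference is planned without baseline adjustment, and with an interval only if the data look normal; adjusting for the baseline score already collected would usually tighten this descriptive estimate

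*SAP*

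**What the plan says.** Protocol 4.2.2 lists among the secondary endpoints "Changes in patient reported abdominal and GI symptoms, dietary habits, and symptom/dietary impact measures". SAP 4.11 measures these with two new instruments, HAP-SS and HAP-DB. On scoring it says: "Each item will be calculated at each evaluation/visit as the mean of the item scores over the seven days previous to the visit". The item means are summed and rescaled to 0-100, giving a HAP-SS total, four HAP-SS domain scores and one HAP-DB total.

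The baseline score is defined and required. SAP 4.11: "The baseline value is defined as the last available measurement prior to the date of the first double-blind study treatment administration". SAP 3.6 restricts the PRO set to treated patients "with a baseline and at least 1 non-missing post-baseline PRO evaluation".

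For the randomised comparison SAP 5.11 says: "During the DBTP the difference in change score from baseline between the treatment groups will be calculated and presented". The output is a mean with a 95% "confidence interval (if data is normally distributed), standard error, median, Q1, Q3, minimum value, and maximum value at each time point". The same paragraph adds: "No formal inferential testing will be performed". It gives no model, covariate, normality criterion or alternative interval.

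By contrast, the primary triglyceride model in SAP 5.7.1 adjusts for the baseline value. Protocol 10.4.3.2 would have carried that approach to continuous secondary endpoints in general, although its sentence on the symptom and dietary measures promises only summary statistics. SAP 1.2.4 (item 5) withdraws the general rule because the repeated-measures model may fail to converge.

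**The concern.** SAP 5.7.2, 5.7.4 and 5.7.5 plan only within-patient tests for lipids, PET and MRI. The PRO contrast is therefore the one secondary efficacy comparison for which the SAP specifies a randomised difference with an interval, so it is worth estimating well. Three features weaken it.

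- **No baseline adjustment.** A change score subtracts the whole baseline value. If baseline and follow-up are imperfectly correlated, that over-corrects: an arm that starts higher by chance tends to show a larger fall. With up to about 50 patients split 2:1, chance differences at baseline are not negligible.
- **A conditional interval.** The 95% interval depends on a normality judgement with no stated test, threshold or fallback. Six scores at three double-blind visits with questionnaires (weeks 4, 8 and 12) give up to 18 such judgements, made after the data are seen. Intervals could be present for some scores and visits and absent for others.
- **Statistics without an estimator.** Median, quartiles, minimum and maximum are requested for a difference between two unpaired groups, without saying how they are to be computed.

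At stake are the width and reproducibility of a descriptive estimate.

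**Working it through.** **Plan's own figure.** There is none to reproduce. SAP 2.2 covers triglycerides, PET SUVmax and an MRI parameter; it gives no SD, correlation or precision target for HAP-SS or HAP-DB.

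**Inputs from the documents.** Up to about 50 patients, 2:1, so about 33 vs 17 (SAP 2.1). A smaller case of 16 vs 8, N=24, is the split used for imaging in SAP 2.2. Cohort 1 has at most about 9 patients (SAP 2.1).

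**Assumed, not in the documents.** Baseline-to-visit correlation ρ; the same SD s at baseline and follow-up; the same slope and residual variance in both arms.

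**Step 1: variances.** With n1 and n2 patients per arm:
- change-score difference: 2s²(1−ρ)(1/n1+1/n2)
- ANCOVA difference, large sample: s²(1−ρ²)(1/n1+1/n2)
- ratio: (1−ρ²)/[2(1−ρ)] = (1+ρ)/2, so the reduction is (1−ρ)/2.

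Large-sample reductions are 45% at ρ=0.1, 35% at 0.3, 25% at 0.5, 15% at 0.7 and 5% at 0.9.

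**Step 2: cost of estimating the slope.** Multiply the ratio by 1+1/(N−4):

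| ρ | N=50 (×1.0217) | N=24 (×1.05) | N=9 (×1.20) |
|---|---|---|---|
| 0.3 | 0.65 → 0.664, 34% less | 0.6825, 32% less | 0.78, 22% less |
| 0.5 | 0.75 → 0.766, 23% less | 0.7875, 21% less | 0.90, 10% less |
| 0.7 | 0.85 → 0.868, 13% less | 0.8925, 11% less | 1.02, 2% more |

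Simulation (20,000 runs per setting) agrees: reductions of 33%, 23% and 14% at 33 vs 17, and 32%, 22% and 10% at 16 vs 8.

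**Step 3: effect on interval width.** At N=50 the SE ratios are √0.664=0.815, √0.766=0.875 and √0.868=0.932, so the interval is about 19%, 12% and 7% narrower.

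**Step 4: unequal SDs.** If follow-up SD is k times baseline SD, the change-score variance is proportional to 1+k²−2ρk and the ANCOVA variance to k²(1−ρ²). Their difference is (1−ρk)², which is never negative: in large samples ANCOVA does not lose, but the gain moves. For ρ from 0.7 to 0.3 it is 51.0% to 58.3% at k=0.7, and 0.9% to 19.5% at k=1.3.

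**Step 5: chance imbalance.** At 33 vs 17 the SE of the baseline mean difference is √(1/33+1/17)=0.30 SD. At ρ=0.5 with equal SDs, a one-SE imbalance shifts the expected change-score difference by (1−0.5)×0.30=0.15 SD. ANCOVA removes that shift.

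**The case against.** The strongest reply is that this output is descriptive by design. SAP 5.11 rules out inferential testing, the protocol's own PRO sentence asks only for summary statistics, and SAP 4.11 says the structure of both instruments is still being tested. No decision rule depends on the interval. All of that stands and limits the importance of the point. It does not justify the less precise estimator: the SAP chose to report a between-arm mean with an interval, and a descriptive estimate also benefits from being as precise as the data allow.

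The convergence reason in SAP 1.2.4 does not answer the point. A single-visit ANCOVA is ordinary least squares, with no repeated-measures covariance matrix to fit.

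Several stronger readings are tempting and are not supported:

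- **A fixed loss of precision.** A reader might infer that the plan gives away 15% to 35% of the variance. That is only (1−ρ)/2 at ρ of 0.7 and 0.3, in large samples with equal SDs. No passage supports those values.
- **Confounding or bias.** Under randomisation the change-score difference is unbiased. Chance imbalance is part of its sampling error; the valid complaint is sensitivity to the imbalance that happens to occur.
- **Lost power.** No PRO test or power statement exists, so none is lost.
- **Impossible statistics.** Differences of medians and Hodges-Lehmann shifts do exist for independent groups. The defect is that the SAP names no estimator; a minimum or maximum of the difference has no evident meaning here.
- **Certain floor effects.** No entry criterion requires current symptoms, and recent acute pancreatitis is excluded (Protocol 6.2), so scores near the floor are plausible. But Protocol 3.2.1 says the population was chosen to make PRO changes more likely to be seen, and no score distribution is given.

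**Conclusion.** The point holds as a modest, worthwhile improvement. The randomised PRO difference is planned without adjustment although every patient in the PRO set has a baseline score, and its interval depends on an unspecified normality judgement. For the overall double-blind comparison, baseline adjustment would usually narrow the interval and would remove the sensitivity to chance baseline imbalance.

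The size depends on quantities the documents do not give. Under equal SDs, common slopes and ρ of 0.3 to 0.7, the net variance reduction is about 34% to 13% at N=50 and 32% to 11% at N=24. Higher correlations or a larger follow-up SD shrink it towards nothing; lower correlations or a smaller follow-up SD enlarge it. In a cohort of 9 it can disappear, so the argument does not extend to the by-cohort summaries. The lack of a rule for the interval and of an estimator for the median and quartiles needs no assumption about ρ.

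**What to change.** Replace the between-group sentence in SAP 5.11 with wording to this effect:

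*For the overall double-blind comparison, at each visit with PRO data, the evinacumab-placebo difference in HAP-SS (total and each domain) and in HAP-DB will be estimated by ANCOVA on the visit score, with treatment and baseline score as terms. The LS mean difference, SE and 95% CI will be reported in all cases; if residuals are clearly non-normal, the CI will be heteroscedasticity-robust or bootstrap. Median, quartiles, minimum and maximum will be reported by arm only. By-cohort PRO summaries remain descriptive and unadjusted.*

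Name one of the two fallback intervals, and how residuals will be judged, before treatment codes are seen. The analysis stays descriptive, with no test added.

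The cost is one paragraph of SAP text and a short program. No new data are needed and no patient is lost, because the change score already requires the same baseline value.
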